7.2 Endpoints

7.2.1 Primary endpoints

Safety and tolerability:

Clinically significant changes in: vital signs (heart rate, blood pressure, respiratory rate, pulse oximetry and temperature), 12-lead ECG, FEV₁, FVC, physical examination, nasal examination, laboratory safety tests (haematology, biochemistry and urinalysis), tolerability questionnaire, AEs and serious AEs (SAEs). Safety endpoints will be assessed up to 7 days after dosing in Part A or up to 14 days after the last dose in Part B.

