9.4 Withdrawal of subjects from the trial

9.4.1 *Withdrawal of subjects*

Subjects are free to withdraw from the trial at any time without giving reasons. Furthermore, the investigator may withdraw a subject for reasons such as intolerance to trial medication, intercurrent illness, need for medication, which is contraindicated, significant non-compliance with the requirements of the trial, or withdrawal of consent. The investigator will assess the reasons for withdrawal as far as possible and will fully record the circumstances and medical details.

9.4.2 *Individual subject stopping criteria (Part B only)*

A subject who meets any of the following criteria will receive no further doses.

- SAE considered related to study treatment.

- alanine aminotransferase (ALT) $\geq 5 \times$ the upper limit of normal (ULN).
- ALT $\geq 3 \times$ ULN and total bilirubin $\geq 2 \times$ ULN or international normalised ratio (INR) of ≥ 1.5 , as per the guidelines for acute liver failure (if a subject meets that withdrawal criterion, serum bilirubin fractionation should be performed).
- ALT $\geq 3 \times$ ULN if associated with the appearance or worsening of rash or hepatitis symptoms (fatigue, nausea, vomiting, right upper quadrant pain or tenderness, fever, rash or eosinophilia). Subjects who have ALT $\geq 3 \times$ ULN and $< 5 \times$ ULN, and total bilirubin $< 2 \times$ ULN, who do not exhibit hepatitis symptoms or rash, can continue in the study (and continue receiving trial medication) as long as they can be monitored weekly until liver chemistries return to within baseline values.
- FEV₁ or FVC of $< 80\%$ predicted or a decrease of $> 20\%$ from baseline
- Peripheral arterial oxygen saturation (SpO₂) of $< 94\%$

Subjects who meet the above criteria will be considered discontinued from dosing. However, the investigator may ask the subject to continue their participation in the study so they can be monitored for safety, PK and immunogenicity, or the investigator may withdraw the subject from the trial.

Subjects will be informed before they agree to take part in the trial that, if they withdraw or are withdrawn:

- the investigator will stop collecting information about them; and
- they can ask the investigator to destroy any identifiable samples taken from them.

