The investigator will ask withdrawn subjects to provide written consent to a follow-up examination, to check that they have come to no harm as a result of taking part in the trial. Provided that the subject agrees, they will undergo, at withdrawal from the trial (or as soon as possible afterwards), the standard medical examination and laboratory tests which they would have undergone had they completed it. The investigator will record in the case report form (CRF) the results of the follow-up examination of withdrawn subjects, if they give their consent for that.

9.4.3 *Replacement of withdrawn subjects*

Withdrawn subjects will be replaced at the discretion of the sponsor and investigator. Replacements for withdrawn subjects will receive the treatment(s) intended for the withdrawn subject.

10 *Treatments*

10.1 *Treatments administered*

Part A: subjects will receive a single dose of Neumifil or placebo.

Part B: subjects will receive once-daily doses of Neumifil or placebo for 7 days.

All doses will be administered intranasally using an Aptar liquid delivery system. Each dose will consist of nasal drops/spray administered as a maximum volume of 0.5 mL to each nostril. Subjects must lie supine for 5 min after dosing. Further details will be provided in a separate manual.

Fasting requirements are described in section 11.

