12.3 Follow-up

Subjects will return to the ward about 7 (Part A) or 14 (Part B) days after their (final) dose of trial medication for a follow-up visit. Withdrawn subjects who consent to a follow-up visit will undergo the same procedures (see section 9.4).

The follow-up period may be extended if:

1. a subject has an unresolved AE at the follow-up visit, which, in the opinion of the investigator, merits further follow-up; or
2. new information becomes available that supports an extended follow-up period.

The investigator will decide on the nature of the follow-up. For example, subjects may have a telephone follow-up at which they are asked about AEs, or subjects may be asked to attend extra outpatient visits for additional monitoring of effects of IMP, and for extra safety tests. The extra safety tests might include tests that are not described in this protocol. The investigator reserves the right, during or after the study, to repeat safety tests or to do any extra safety tests that are in the best interest of the subjects. Those extra tests may or may not be described in this protocol.

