14.3 Procedures for dealing with serious adverse events

In the event of any SAE which, in the investigator's opinion, justifies termination or modification of the trial (see section 8.4), dosing will be stopped and the sponsor's responsible physician will be informed immediately (within 24 h of the investigator becoming aware of the event) by telephone or email, as follows.

Sponsor's
responsible
physician:

Tel:

Email:

All SAEs occurring after the signing of the ICF until the follow up visit, regardless of study drug relationship, must be reported to the sponsor's pharmacovigilance provider, with as much information as possible, within 24 h of the investigator becoming aware of the event. The investigator will complete a serious adverse event form and provide it to the sponsor's pharmacovigilance (PV) provider immediately (and within 24 hours of becoming aware of the event), via the following contact details.

Diamond PV Services Limited

Email (primary): [contact]
Fax (back-up): [contact]
Tel (back-up): [contact]

The sponsor will also be notified by email [REDACTED]

The investigator will notify the REC of SAEs that occur during this trial, if applicable, in accordance with the SOPs issued by the Research Ethics Service (RES).

The sponsor is responsible for determining the expectedness of the event, using the reference safety information in the IB. The sponsor will notify the MHRA of all suspected unexpected serious adverse reactions (SUSARs) and will be responsible for ensuring that the REC is notified of SUSARs, if applicable. SUSARs that are fatal or life-threatening must be notified to the MHRA and REC within 7 days after the sponsor has learned of them. Other SUSARs must be reported to the REC and MHRA within 15 days after the sponsor has learned of them.

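### Section 9.4.2 stops data collection for subjects the investigator withdraws as if they had withdrawn consent, so safety follow-up can end before the primary window closes

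*Combined protocol and SAP*

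**What the plan says.** Section 9.4.1 lets the investigator withdraw a subject and names intolerance to trial medication first among the reasons. Section 9.4.2 lists Part B criteria for ending an individual's dosing: a related SAE, liver tests, spirometry and oxygen saturation. A subject who meets one is discontinued from dosing. The investigator may then ask the subject to stay in the study for safety, PK and immunogenicity monitoring, "or the investigator may withdraw the subject from the trial".

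The same section sets out what subjects are told will happen "if they withdraw or are withdrawn": "the investigator will stop collecting information about them". It does not separate the two kinds of withdrawal.

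Three places deal with what follows:

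- **Section 9.4.** Withdrawn subjects are asked for written consent to a follow-up examination. Those who agree have, "at withdrawal from the trial (or as soon as possible afterwards), the standard medical examination and laboratory tests" that completers would have had.
- **Section 14.4.** For withdrawals due to AEs, the examination is placed at withdrawal.
- **Section 12.3.** "Withdrawn subjects who consent to a follow-up visit will undergo the same procedures", with a reference back to section 9.4 and no timing of its own for these subjects.

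Section 7.2.1 sets the primary safety window at 7 days after dosing in Part A and 14 days after the last dose in Part B.

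**The concern.** Withdrawal of consent ends the right to collect data. Withdrawal by the investigator does not, yet the plan gives both the same consequence. Intolerance is a named reason for the second kind, so the subjects whose follow-up may be cut short include those who tolerated the product worst. That makes the missing follow-up potentially informative.

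At stake is the late part of the primary endpoint: new or worsening events, and evidence of recovery, between withdrawal and the end of the window. Recovery matters in this trial. Sections 6.2.5 and 6.5 rely on the airway and nasal inflammation in rats having resolved after two weeks off treatment, and follow-up after stopping is where human evidence of reversibility would come from. Section 16 does not say how incomplete follow-up will be handled. Withdrawn subjects stay in the denominator of the AE tables although they were not observed for the whole window.

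**Working it through.** The plan has no figure to reproduce. Section 16.1.2 states that no hypotheses are tested, section 16.2 gives no sample-size calculation, and no withdrawal rate appears. The check is a reading of the text followed by an illustration of size.

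**Step 1: trace each type of subject.**

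- *Withdraws consent.* Collection stops. This is appropriate.
- *Meets a listed Part B criterion.* Dosing stops. If the investigator asks and the subject agrees, the outpatient and follow-up visits continue. If the investigator withdraws the subject instead, the data stop applies.
- *Withdrawn by the investigator for another reason, such as nasal intolerance.* The option to stop dosing but stay in the study is written only for the listed criteria, and nasal intolerance is not one of them. The data stop applies.

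The data-stop text sits under a heading marked Part B only, but its wording is general. I read it as applying to any withdrawal.

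**Step 2: compare the timing.** Sections 9.4 and 14.4 both place the examination at withdrawal, and section 9.4 adds as soon as possible afterwards. Section 12.3 supplies the procedures but sends the reader back to section 9.4. None of the three sets the examination at 7 or 14 days after the last dose for a withdrawn subject.

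**Step 3: size of the loss.** Inputs are a 14-day Part B window (7.2.1) and 6 active subjects per Part B group (8.1.2). Planned active person-days after the last dose are 6 × 14 = 84 per group. If one subject is last seen k days after the last dose, the share lost is (14 − k)/84.

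| k (days) | Window days observed | Share of group's active person-days lost |
|---|---|---|
| 0 | 0 of 14 | 14/84 = 16.7% |
| 1 | 1 of 14 | 13/84 = 15.5% |
| 7 | 7 of 14 | 7/84 = 8.3% |

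Two such subjects at k = 0 give 28/84 = 33.3%. The corresponding extreme in Part A, with its 7-day window, is 7/(4 × 7) = 25% in Groups A1–A3 (4 active) and 7/(6 × 7) = 16.7% in Groups A4–A5 (6 active).

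**Step 4: what one lost subject does to late-event detection.** Assume a per-subject rate p of a late event, independent of who is lost. The chance of seeing at least one is 1 − (1 − p)^n.

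| Assumed p | n = 6 followed | n = 5 followed |
|---|---|---|
| 10% | 46.9% | 41.0% |
| 20% | 73.8% | 67.2% |
| 30% | 88.2% | 83.2% |

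With no events seen, the exact two-sided 95% upper limit is 1 − 0.025^(1/n): 45.9% for 0/6 and 52.2% for 0/5. If the lost subject is the one at highest risk, the loss of information is greater than these figures show.

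**The case against.** The best defence is that the protocol already separates ending dosing from leaving the trial. For a liver, lung or oxygen signal, the first option it names is continued monitoring, and a volunteer can only be asked. That stands, and it makes the loss possible rather than certain. It does not settle the matter, because retention is discretionary and does not reach intolerance outside the listed criteria.

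Several stronger readings are tempting, and the documents do not support them:

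- *A reader might infer that no spirometry, nasal examination or ADA sample would be obtained after withdrawal.* Section 12.3 gives consenting withdrawn subjects the follow-up procedures, and the Part B schedule in section 12.1.2 includes all three at follow-up. What is open is when they happen, and the loss of the outpatient visit.
- *A reader might infer that the intolerance itself goes uncounted.* Section 9.4.1 requires the circumstances and medical details to be fully recorded. Section 16.1.6.1 lists AEs leading to withdrawal separately, and section 16.1.3 keeps every dosed subject in the safety population. Only later events can be missed.
- *A reader might see a contradiction with section 14.3*, under which "All SAEs occurring after the signing of the ICF until the follow up visit, regardless of study drug relationship, must be reported". That duty runs from the investigator becoming aware of an event and can operate after scheduled collection ends. It softens the concern for SAEs but not for non-serious events.
- *A reader might infer that sites would withdraw subjects in order to replace them*, since section 9.4.3 says "Withdrawn subjects will be replaced at the discretion of the sponsor and investigator". Replacement is discretionary, and section 8.5.1 needs data from only 6 of the 8 subjects in a Part B group, so nothing in the text creates that pressure.
- *A reader might infer that an ADA sample taken early at withdrawal is worthless.* The documents give no basis for judging this.

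Section 12.3 also allows follow-up to be extended for an AE unresolved at the follow-up visit. This is at the investigator's discretion and does not restore routine observation to the end of the window.

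**Conclusion.** The point holds in limited form. As written, one rule covers withdrawal of consent and withdrawal by the investigator, and no section requires a subject withdrawn by the investigator to be observed to the end of the primary safety window. The data at risk are new or worsening events and evidence of recovery after withdrawal, with the risk weighted towards less tolerant subjects.

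The 16.7% figure in Part B is an upper bound for one withdrawn subject. It assumes withdrawal and examination on the day of the last dose, no replacement and no continued monitoring, and it shrinks as the examination moves later. The detection figures rest on assumed event rates. With no withdrawal rate in the documents, the expected loss cannot be estimated. The claim that AE counts at a poorly tolerated dose will be biased downward goes further than the text allows: missed late events are possible, but how many cannot be said.

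**What to change.** 1. In section 9.4.2, limit the end of data collection to subjects who withdraw consent.
2. State that subjects stopped or withdrawn by the investigator who still consent are, by default, followed at the existing outpatient (Part B) and follow-up visits. Time these from the last dose received and continue to the end of the primary safety window in section 7.2.1.
3. Give the follow-up examination of withdrawn subjects one consistent timing across sections 9.4, 12.3 and 14.4.

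The cost is protocol and information-sheet wording, plus attendance by a few stopped subjects at visits already in the schedule. No dose or stopping criterion changes, and subjects keep the right to withdraw consent at any time.

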10.2 Overdose

Symptoms of overdose of Neumifil are not yet known. In the case of accidental overdose, subjects should be treated symptomatically as no specific antidote is available.

10.3 Blinding

The trial medication will be repackaged and relabelled by the HMR Pharmacy, according to the randomisation schedule. Active and placebo treatments will be labelled such that it is not possible to distinguish between them. If the expiry dates of placebo and active treatment differ, both treatments will be labelled with an expiry date no later than the earlier of the 2 expiry dates. Each subject's treatment will be given a unique code number, traceable to the batch number of the medication.

The placebo and active treatments for each group will be identical in appearance, and similar in taste and smell. To maintain the blind nature of the trial, in each group, the number of sprays of placebo treatment will be the same as active treatment.

A sealed copy of the randomisation code will be kept in a locked file in the HMR Pharmacy. A copy will also be kept by the bioanalytical laboratory. The investigator will be supplied with sealed envelopes, each one containing the treatment allocation for the subject whose number appears on the outside of the envelope. Those envelopes will be kept in the trial master file, readily accessible to clinical staff. Sealed individual code break envelopes will also be provided to the Pharmacovigilance Service Provider. Emergency procedures for revealing medication codes are specified in section 10.4.

The investigators, medical monitor and clinical monitor will remain blinded throughout the trial, unless safety concerns necessitate unblinding (see section 10.4 below).

10.4 Unblinding procedure

If unblinding is required in the interest of the safety of a subject (for example, in a medical emergency where the identity of the investigational material will affect the management of the subject), the principal investigator or delegate will open the individual code-break envelope for that subject without prior consultation with the

sponsor. In that event, the principal investigator or delegate will notify the sponsor as soon as possible (within 24 h) that the randomisation code has been broken for the subject. If unblinding may be helpful, but is not required immediately (for example, the information may be useful to make decisions for other subjects in the group), wherever possible, an investigator will discuss the matter with the sponsor before opening any individual code-break envelopes.

When the trial database for the relevant study part has been locked, the HMR statistician will inform the sponsor of his or her intention to break the randomisation code. The statistician will break the code, and do the statistical analysis of the relevant data.

10.5 Method of assigning subjects to treatment groups

Volunteers will be assigned a unique screening number, from 001 onward, at their screening visit. After passing all of the screening assessments, subjects will be allocated to study part and group, as described below, according to their availability and the scheduled trial dates.

Subjects will be numbered consecutively, in the order in which they arrive on the ward and are entered into the trial. Subject numbers are presented in Table 4. Subject numbers will be allocated to treatments (active or placebo) according to a randomisation schedule prepared by an independent HMR statistician, using a SAS program.

Subject numbers, and sentinel subject numbers for Part A, are provided in Table 4; at each dose level, subjects will receive active or placebo treatment as described in section 8.1.

Randomisation is described further in section 8.1.

Table 4 Subject and sentinel numbers

Study part	Group	Subject numbers	Sentinel subjects
A	A1	1001–1006	1001 and 1002
	A2	1007–1012	1007 and 1008
	A3	1013–1018	1013 and 1014
	A4	1019–1027	1019 and 1020
	A5	1028–1036	1028 and 1029
	A6*	1037–1045	1037 and 1038
	A7*	1046–1054	1046 and 1047
B	B1	2001–2008	–
	B2	2009–2016	–
	B3	2017–2024	–
	B4*	2025–2032	–

* optional groups.

Replacements for withdrawn subjects will be given a number equal to that of the subject that they replaced plus 100. So, Subject 1001 would be replaced by Subject 1101, and Subject 2025 would be replaced by Subject 2125, and so on.

10.6 Selection and timing of dose for each subject

The treatments to be administered are described in sections 8.1 and 10.1. Subjects will be randomly assigned to those treatments, as described in section 10.5 above.

Because Neumifil has never been given to humans before, each new ascending dose in Part A will be staggered as described in section 8.1.

In Part A, all doses will be given in the morning. In Part B, doses will be given once or twice-daily at the same time each day (\pm 15 mins from the time of dosing on Day 1).

10.7 Previous and concomitant treatment

Restrictions on previous medication are described in exclusion criterion 14.

During the trial, concomitant medication may be given if the subject's GP believes it to be necessary. In addition, up to 4 doses of 500 mg paracetamol will be allowed per day for mild analgesia. No COVID-19 vaccine is allowed during the 7 days before the first dose of trial medication or the 7 days after the final dose of trial medication. Any other concomitant treatment will be given only if deemed strictly necessary by the investigator or co-investigator. In any case, all concomitant treatments will be reported in the CRF along with their daily dosage, duration, route of administration, and reasons for administration. Subjects who have received any concomitant treatment may be withdrawn from the trial at the discretion of an investigator.

10.8 Assessment of compliance

Subjects will be dosed on the research ward under the supervision of 2 suitably trained members of HMR staff.

11 Dietary and lifestyle restrictions

Subjects will abide by HMR house rules while on the ward.

Part A

Subjects will fast (no food or drink other than water) overnight for \geq 8 h before dosing until 2 h after dosing on Day 1. Standard meals will be provided at about 2, 4 and 10 h after dosing.

Part B

Morning dose: Subjects will fast (no food or drink other than water) overnight for ≥ 8 h before dosing until 2 h after dosing on Day 1 and Day 7. Standard meals will be provided at about 2, 4 and 10 h after dosing on Day 1 and Day 7.

Evening dose (if applicable): Subjects will fast (no food or drink other than water) for at least 2 h before and 2 h after dosing on Day 1 and 7.

At all other times during the study, standard meals will be given at usual times.

All study parts

During the study, subjects will fast for at least 8 h before laboratory safety blood samples are taken at screening, on admission (Day -1), and Follow-up.

No alcoholic drinks or smoking will be allowed during the period from 24 h before admission until follow-up. No caffeinated drinks will be allowed from 24 h before admission until discharge from the ward (Day 2 in Part A and Day 8 in Part B). No strenuous exercise will be allowed from 2 days before screening until follow-up.

Subjects will rest in bed in the supine position during and until ≥ 5 min after dosing.

Subjects must not sunbathe or use a sunbed during the study.

Subjects must use a reliable method of contraception¹⁰, as follows.

Men

Male subjects must not plan to father a child, or donate sperm, from dosing until 3 months after their (last) dose.

Male subjects must not have sex without using a condom, from dosing until 3 months after their (last) dose, if their partner is a woman of childbearing potential. They do not need to use any contraception if: they've had a vasectomy, and surgical success has been confirmed by medical assessment; their partner has had a bilateral tubal ligation; or their partner is not of childbearing potential. Partners who are not of childbearing potential are defined as: men; post-menopausal women (no menstrual periods for at least 12 months); or women who have no uterus, ovaries or fallopian tubes.

Women

Women of childbearing potential must use a highly effective method of contraception with low-user dependency during the trial, and for up to one month after the final follow up visit. They must have been using that method for at least 28 days before the start of the trial. Highly effective methods of contraception include:

- Progestogen-only hormonal contraception implants associated with inhibition of ovulation
- Intrauterine device (IUD)

- Intrauterine hormone-releasing system (IUS)
- Bilateral tubal occlusion or ligation
- Vasectomised partner (with surgical success confirmed by medical assessment)

A woman is considered to be of non-childbearing potential if she meets one of the following criteria:

- is post-menopausal (the last menstrual period was at least 12 months ago, and Follicle Stimulating Hormone (FSH) test at screening confirms post-menopausal status)
- has no uterus, ovaries or fallopian tubes

Women who are taking HRT must use contraception (as described above) during the trial unless prescribed following bilateral oophorectomy, hysterectomy or salpingectomy.

Combined or progesterone-only hormonal contraception associated with inhibition of ovulation (oral, intravaginal, transdermal or injections) are not allowed.

Subjects who practise true abstinence or who only have same-sex relationships need not use contraception, provided it is in line with their preferred and usual lifestyle (note: periodic abstinence [eg calendar, ovulation, symptothermal, and post-ovulation methods] and withdrawal are not acceptable methods of contraception). Should any such subject stop practising true abstinence, they must use contraception as described above.

12 Procedures and observations

Only subjects who meet all the inclusion and no exclusion criteria will be eligible for enrolment into the trial (see section 9). Each subject will be allocated a unique trial number (see section 10.5).

Additional time points may be introduced, and changes to time points may be made, in accordance with section 12.2.

The following assessments will be made at the timepoints given in sections 12.1.1 (Part A) and 12.1.2 (Part B).

Safety and tolerability

Laboratory assessments (haematology, biochemistry and urinalysis), physical examinations, 12-lead ECGs, vital signs (heart rate, blood pressure, respiratory rate, pulse oximetry and temperature), nasal examinations and spirometry will be done before and during dosing and frequently until the subject's last visit in each study part. Subjects will complete a tolerability questionnaire post-dose after each dose of Neumifil. AEs will be recorded from screening until the subject's last visit in each study part.

The schedules of procedures are in sections 12.1.1 (Part A) and 12.1.2 (Part B).

Laboratory safety variables to be assessed during the study are in Table 7.

Throughout the study, AEs and concomitant medication will be documented as they are reported by the subjects. Subjects will be questioned about AEs when procedures are done, and when they return to the ward for outpatient visits (Part B only), and at follow-up.

Plasma concentration of Neumifil

Blood samples for assay of Neumifil will be taken before and up to 3 h after dosing on Day 1 (Part A) and Days 1 and 7 (Part B).

[figure not shown]
Immunogenicity

Blood samples for assay of Neumifil ADAs will be taken before dosing on Day 1 and on Day 22 (Part B only).

